## **3. Enrollment & Tracking**

Once participant contact info has been shared with MSM researchers in the secure study portal, MSM will use the portal to track:

- a) Participant contact
- b) Final screen failures
- c) Consent / Enrollment Status
- d) Participant dropouts
- e) Withdrawal of participants from study
- f) Termination of participants from the study

This will allow HMS to track interactions of former players with MSM researchers to maintain awareness of potential participant burden, to consider the discontinued participants for other HFPHS studies, and to consider this information in relation to other ongoing projects.

#### **4. Randomization**

After pre-testing of the first 10-24 participants, they will be randomly assigned to either the Immediate ImT group (n=5-12) for immediate training or to the Delayed DeT control condition (n=5-12). The method of randomization is a balanced randomized block design with 1:1 allocation to either receiving the GRIT immediate ImT training intervention or the Delayed DeT control condition. A stratified permuted block design randomization scheme will be pursued with a variable but masked block size. A one–two stratification factors will be considered for selection from position played, age, and baseline severity of pain. The randomization protocol will further dictate inspection of balance of these factors between the two groups every ten recruited participants.

#### **5. Intervention Training**

There will be two Immediate Training ImT groups of 5-12 participants per training group and two Delayed Training DeT control groups with 5-12 participants in each group. One Immediate ImT intervention group will be trained at one time for 4 weeks with 2 biweekly sessions, followed by post-testing. During this time the Delayed DeT group waits, since only one group can be trained at one time. The Delayed DeT group will receive training after waiting 4 weeks and a first post testing session. At the end of its training, the DeT group will receive a second post-testing session.

Training sessions will be held at the Morehouse School of Medicine in the Research Wing. There will be two 90-minute training sessions per week, taking place between 4-6pm on two days out of Mondays through Thursdays. The exact days and times of the training will be set in advance for each group, and will not be accommodating of individual schedules.

Should a participant miss a scheduled training session or be unable to complete a session in full, the attendance requirements are as follows:

Participants are allowed to miss 2 out of 8 sessions. They are also given the option to make up one or both sessions. They are allowed to make up a maximum of 2 sessions. If they miss a 3rd session, they are not allowed to make it up but can stay in the study. If they miss a 4th session, they will be terminated from the study. The content of the makeup sessions will follow the content of the modules: (1) introduction to concepts (2) illustrative examples (3) applications to own life with exercises. Makeup sessions will be one-on-one with the interventionist, and will last no more than 30 minutes. Participants will be compensated for makeup sessions as they are for group training sessions they attend.

If a participant attends but cannot complete a training session, it will be considered a missed session if they leave before the half-way time point (45 minutes). In this case the above policy regarding missed sessions will apply. If they leave the training session after 45 minutes, they may complete the rest of the session as a homework assignment, since homework

assignments are practiced at the end of each session. Participants will only be compensated for incomplete sessions if they attend for at least half (45 minutes).

GRIT intervention training is a hands-on group experiential simulation and repeated practice that takes participants back to their earlier goal-directed experiences and then applies these to episodes of pain and suffering. Participants are asked to identify engagement and social relatedness (the goal-directed resources) from childhood or early adulthood, to re-experience these in descriptions and sensations, then take these episodes into experiences of pain or trauma, thereby transforming negative episodes into instances of personal resilience. At the end, participants are asked to design and implement a good life for themselves. In this manner, the past is used to construct a future, and goal-directed responding is replacing stimulus-guided responses to fear or pain. A manualized program consists of four modules that cover engagement, social relatedness, transformation, and making a good life, shown in Table 4. The manual is provided in Appendix 4.

Table 4. A Modular Program for Goal-Directed Resilience Training (GRIT)

Introduction	Introduction and Psychoeducation Main elements: engagement, relatedness, transformation, building a good life
Module I	Approach/Engagement Consists of interest, curiosity, appreciation, noticing beauty. Find examples from childhood/early adulthood of interest, curiosity, etc. Describe examples, what the senses are doing, make a visual representation. Review written and visual examples, do activities, do homework assignments
Module II	Social Relatedness Consists of empathy, compassion, helping, friendship, love. Find examples from childhood/early adulthood of empathy, helping, etc. Describe examples, what your senses are doing, make a visual representation. Review written and visual examples, do activities, do homework assignments
Module III	Transformation Return to pain or traumatic event with an example of engagement or relatedness. Identify pain or stressful event you wish to return to. Be in that scene or pain as (e.g. holding the first frog in your hand when you were five while retelling a battle scene in Vietnam, etc.) Reading examples of transformation, do activities, do homework assignments.
Module IV	Building a Good Life Imagine and describe a life well lived. Describe a good life for yourself, with engagement, with social relatedness. Create opportunities for growth when pain has limits and stunts growth. Reading examples and activities for creating a good life are provided.

For each Module the training follows the same format. The content is covered in 3 parts: (1) Main concept to be covered in the module, (2) Examples of the concept in readings (3) Exercises that apply the concepts to personal experiences. Completion of the exercises are started in the training class and assigned to be completed as homework and to be turned in the following week.

## **6. Homework**

The Study Workbook (within Appendix 6) contains all assignments, practice exercises, and instructions. Each module is to be completed in two sessions of one week. Homework is assigned at the beginning of each week and to be turned in at the beginning of the next week. For each module, the homework asks participants to find examples from their lives of the main concept covered in that module, note their sensory reactions, and apply the examples to change how they experience pain and stress.

The Habit Maker Checklist tracks the application of training concepts and activities in participants' everyday life. Participants are to complete one checklist for each week.

Completion of The Study Workbook and the weekly Habit Maker Checklist questionnaire are required of all participants, and participants may be withdrawn from the study if they are not completing their homework assignments.

## **7. Control Condition**

As previously described, the control condition is the Delayed DeT group that waits for 4 weeks while the Immediate ImT group experiences the GRIT training. At the end of the four weeks of training of ImT and waiting of DeT, both groups are post-tested. At that point the Delayed DeT group receives the GRIT training and then a second post-testing.

## **8. Post-Testing**

Following completion of 4-week training, the immediate ImT participants and Delayed DeT controls will be scheduled for post-intervention assessments, listed in Table 2. These will be nearly identical to the pre-intervention assessments, will last 90-120 minutes, and will occur within 2 weeks of the final treatment session. In case of extreme emergencies, if a participant cannot schedule their post-testing session within 2 weeks of completing the training, post-testing can be extended by another 2 weeks for no more than a total of 4 weeks from training completion. Delayed DeT Controls will receive training after their first but before a second post-testing session.

## **9. Length of Study Enrollment**

A participant may be enrolled in this study from 6-18 weeks

## **10. Compensation & Reimbursement**

Per participant, compensation will consist of \$75 for their enrollment & pre-testing visit (\$25 if they are not eligible for the study after final screening), \$75 per training session for a total of \$600/8 sessions, and \$75 for their post-testing session. The control group will receive a second \$75 payment for second post-testing session. The total payment for each of the groups will equate to \$750 for the ImT group (experimental) and \$825 for the DeT group (control). Payment will be made at the end of each testing session and at the end of the completion of all training sessions. Missed sessions will be offered as makeup sessions of no more than two makeup sessions. Participants will be paid for makeup sessions. Participants will be paid for all training sessions they attend, regardless of whether they complete the study requirements of 8 sessions & post-testing. Method of payment will be by ClinCard, which works like a debit card. They will receive the ClinCard after their enrollment session at MSM, and it will be reloaded at each payment time. They will be able to use the funds in approximately 1 business day. This is to repay participants for time spent in the study and any inconvenience.

### Participant Parking

The Morehouse School of Medicine has a parking deck available to visitors and study participants for a total cost of \$5 per visit between the hours of 7:00am-5:00pm Monday-Friday. If they are driving, participants will pay out of pocket for the cost of parking when they attend each of the study sessions. The highest amount of cost for parking that a participant would incur would amount to \$55. The compensation being provided for their participation in the study is intended to offset any incurred costs to the participant.

### Compensation Summary

Final screen & pre-testing- 90-120 minutes: \$75

For participants who attend but who are found not to be eligible for the study: \$25

Per training session- 90 minutes: \$75

Total for 8 sessions = \$600

Post-testing session- 90-120 minutes: \$75

2nd post-testing session (for delayed control group only): \$75

### Totals

Immediate experimental group: \$750

Delayed control group: \$825

[figure not shown]
### Timeline

The timeline for Group 1 (ImT) and Group 2 (DeT) is summarized in Table 5 below. The time course of the steps involved in this study are shown in the timeline diagram.

Table 5. Timeline

Timeline			
Mo	Intervention	Mo	Intervention
1	Recruitment Group 1	8	Training ImT 2 (N=5-12)
2	Pre-Test 1 (N=10-24); Random Assignment	9	Post-Test 1 (N=10-24)
3	Training ImT 1 (N=5-12)	10	Training, DeT 2 (N=5-12)
4	Post-Test 1 (N=10-24)	11	Post-Test DeT 2 (N=5-12)
5	Training, DeT 1 (N=5-12)	12	Data Analysis
6	Post-Test DeT 1 (N=5-12); Recruitment Group 2	13	Write-up
7	Pre-Test 2 (N=10-24); Random Assignment		

## Timeline for Group 1 Intervention and Control

## **Quality Monitoring of the Study**

Blinding Monitor to assure that participants and person conducting the testing are blind as to intervention and control conditions.

Fidelity Monitor will assure that therapists will conform to the method as set out in the modularized program.

Workbook includes all homework assignments

Habit Maker Checklist will monitor application of program content to daily life.

Workbook Log tracks completed homework

Appendix 6 includes the above items: (1) Monitors – Blinding, Fidelity, (2) Homework – Workbook, Habit Maker Checklist, (3) Homework Log.

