## OVERVIEW AND BACKGROUND

1. Chronic pain is a national medical problem and priority as evidenced by the massive opioid epidemic. For former professional football players, chronic pain can be the dominant condition of life, degrading its quality in multiple domains. We propose to address chronic pain with a resilience skills training intervention to improve functions affected by pain, i.e., quality of life, personal relationships, and personal growth or development. The specific aim of this study is to test an intervention to decrease chronic pain and comorbid symptoms and improve a broader adaptive level of functioning through Goal-Directed Resilience Training (GRIT) for chronic pain. We hypothesize:
  - a. GRIT training intervention versus control training will be associated with reduced chronic pain and related symptoms of insomnia, anxiety, depression, improved emotional functions, and improved neurocognitive functions.
  - b. Improved self-reported physical health, quality of life, personal relationships, and personal growth will be evident for intervention versus control participants.

Although the body as internal environment is long recognized as such (*milieu intérieur* of Claude Bernard, 1865 in Gross 1998; interoception, Craig, 2009), our approach is innovative in treating pain as an internal interoceptive environment, one that is characterized by unpredictability and aversiveness. These two qualities also define extreme environments, be these extremes of weather or prisoner of war camps. Resilience, if thought of as a process as well as a state, buffers against the harshness of the environment, facilitating success and thriving in the midst of adversity. The engine that drives, maintains, and increases pain is unpredictability. The unpredictability of pain (in terms of intensity, timing, duration, physical and social context, etc.) makes it a powerful, variable, and often unstoppable force. We propose an interactive model of Environment x Biobehavioral Control in which chronic pain and resistance or resilience to pain are embedded. We believe this model explains the preliminary successes and points to the promise of our GRIT intervention.

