## PROJECT DETAILS

### Experimental Design and Methods

#### Intervention Training for Former Players

Between 20 to 48 eligible and consented participants from the Atlanta area will be identified (with a goal of 40 completing the study). They will undergo a pre-training test session and will then be randomized to either the Immediate GRIT (ImT) training intervention or the Delayed Training (DeT) control. At this time there will be one intervention immediate (ImT) group and one delayed (DeT) control group of 5-12 participants per group. The immediate (ImT) group will be trained for 4 weeks with 2 biweekly sessions. At the end of GRIT training they will be post-tested. The delayed (DeT) group wait during these 4 weeks and do not receive training. At the end of the 4-week waiting period, they will also be post-tested. At this point, they will be offered GRIT training for 4 weeks with 2 biweekly sessions. At the end of their training, they will be given a second post-testing. This process will then be repeated for two additional groups of 5-12 ImT and 5-12 DeT participants.

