Goal-Directed Resilience Training (GRIT) is a hands-on experiential simulation and repeated practice that takes the person back to his/her earlier goal-directed experiences and then applies them to episodes of pain and suffering. The brain is inherently a simulation device where actual and simulated actions activate the same cortical areas (e.g. Decety & Grèzes, 2006). Goal-directed responding is inhibited by stimulus-guided responses to fear or pain. The restoration of goal-directed engagement and relatedness are natural capacities we have for pain control (Erpelding & Davis, 2013). This is the main focus of the training. Participants are asked to identify engagement and social relatedness (the goal-directed resources) from childhood or early adulthood, since these early years are formative, as well as examples from present time. They are asked to re-experience these in descriptions and sensations, then take these episodes into experiences of pain or trauma, thereby transforming these into resilience. This is accomplished through a manualized program consisting of four modules: engagement, social relatedness, transformation, and defining a good life. GRIT training is a small-group intervention consisting of 5-12 participants per group. We propose a pilot study of 20-48 participants or 4 groups with 2 intervention and 2 control conditions to be conducted in Atlanta. Up to eight (8) subjects beyond our goal of 40 will be added to make up for attrition. Individuals randomized to control condition will participate in the GRIT the training after post-assessment. Training extends over 4 weeks, consists of 90-minute biweekly visits, for a total of 8 visits.

**Outcome Measures.** To test hypotheses 1 and 2, outcome measures for GRIT training include focused pain-relevant symptom measures, adaptive functions measures, neurocognitive measures, and PACE, as listed in Table 2. List of outcome measures are provided in Appendix 1.

Table 2. Proposed Outcome Measures for GRIT Training

Focused Pain-Relevant Measures	
Pain Outcome Questionnaire (POQ), (20 items)	
PROMIS Pain Interference Short Form. (8 items)	
PROMIS Sleep Impairment (8 items)	
PROMIS Sleep Disturbance (8 items)	
Pain Catastrophizing Scale, (13 items)	
Chronic Pain Acceptance Questionnaire, (8 items)	[time to completion = 23 minutes]
Adaptive Functions Measures	
Physical Health: SF-36 Health Measure: physical & mental health, (36 items)	

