**Statistical Considerations**

Design. This is a balanced randomized block design. Twenty (20) to forty-eight (48) eligible and consenting participants from the Atlanta area will be identified from the cohort of research participants at the Football Players Health Study (FPHS) at Harvard University in Boston, MA. They will be selected based on answers previously given to specific FPHS survey questions listed below. They will undergo a pre-training test session and consequently be randomized with 1:1 allocation to either the Immediate GRIT training (ImT) intervention group or the Delayed (DeT) training control group. There will be two Immediate (ImT) intervention groups of 5-12 participants per training group and two Delayed training (DeT) control groups with 5-12 participants in each control group.

Outcome measures (c.f. Table 2). Sample Size and Power. This is a pilot study. Using focused pain-relevant or adaptive measures as outcomes with effect size (minimally detectable differences in weighted scores between the ImT experimental and DeT control group, scaled by pooled standard deviation) of 1, 2, 3, and 4, a regression model with treatment, age and block as effects and an overall 0.05 significance level, 20 participants per group yields an 0.80 statistical power.

For all analyses intent-to-treat principles will be adopted for those who drop out. Pre-treatment scores will be used to generate sampling frames consistent with a multiple imputation approach (Rubin, 1999) to determine post-treatment values.

Statistical Analyses. Summaries will rely on means, standard deviations for continuous variables and frequency and percentages for categorical ones. Univariate analyses for weighted scores and continuous variables groups comparisons will rely on t-tests (if normality assumptions are upheld) and/or non-parametric testing. Categorical variables will be compared using Chi-square/Fisher exact/McNamer testing. Multivariate analyses for the responses of scales/subscales weighted scores, factoring in covariates effects on interventions vs. control, age, block, pre-treatment scores, will use the Generalized Linear Mixed Modeling (GLMM) approach that will allow blocks as random effects and grant each subject their own intercept. All analyses will be conducted using SAS version 9.4

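### The plan says participants are blind to condition, but in a waiting-list design they know their arm once randomised; limit the claim to testers at the first post-test

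*Combined protocol and SAP*

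**What the plan says.** The blinding statement is in the Combined protocol and SAP, under Quality Monitoring of the Study: "Blinding Monitor to assure that participants and person conducting the testing are blind as to intervention and control conditions". It covers participants as well as testers. The Psychiatry Residents role description gives a reason for blinding the people who administer the tests and does not mention participants.

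The comparator is described in several places:

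- **Overview and Background.** Hypothesis (a) reads "GRIT training intervention versus control training will be associated with reduced chronic pain". Hypothesis (b) says that improvements "will be evident for intervention versus control participants".
- **Intervention Training for Former Players.** The delayed (DeT) participants "wait during these 4 weeks and do not receive training". The same section adds: "Individuals randomized to control condition will participate in the GRIT the training after post-assessment".
- **5. Intervention Training.** "During this time the Delayed DeT group waits, since only one group can be trained at one time". Session days and times are fixed beforehand for each group.
- **7. Control Condition and 8. Post-Testing.** The control is the delayed group that waits. Its training falls between its first and second post-tests.
- **Statistical Considerations.** The sample-size paragraph refers to "differences in weighted scores between the ImT experimental and DeT control group", so the planned contrast is immediate against delayed training.

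**The concern.** A statement that participants are blind tells the reader that expectation and knowledge of treatment have been balanced between the arms. Most of the outcomes in Table 2 are questionnaires that participants complete about their own pain, sleep, mood, stress and well-being, and knowledge of treatment can influence such answers. If participants know their arm, a difference at the first post-test combines the content of GRIT with group contact and expectation, and the design cannot separate them.

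That is the ordinary limit of a waiting-list comparison and is acceptable in a pilot if it is stated. Here the blinding sentence says the opposite, and the wording of hypothesis (a) can be read as naming a second kind of training. A reader relying on those two sentences would expect a stronger conclusion than the trial can give. Future Plans says the pilot will provide preliminary data and be followed by a further funding proposal, so the description of the contrast is likely to be carried forward.

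**Working it through.** The plan gives no figure that depends on participant blinding, so there is none to reproduce. The check sets the sections side by side.

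**1. What each arm experiences before the first post-test.**

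| | Immediate (ImT) | Delayed (DeT) |
|---|---|---|
| Pre-test | before randomisation | before randomisation |
| Next 4 weeks | 2 sessions a week | waits, no training |
| Sessions by first post-test | up to 4 × 2 = 8 | 0 |
| Group time by first post-test | up to 8 × 90 min = 720 min = 12 h | 0 h |
| Training after first post-test | none | the same 8 sessions are offered |

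The sources are Intervention Training for Former Players and implementation sections 4, 5, 7 and 8. Table 5 agrees. In the first cohort, immediate training is in month 3, the post-test of both arms in month 4 and delayed training in month 5. In the second cohort these fall in months 8, 9 and 10.

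**2. Can a participant be unaware of the arm?** Masking would have to hide from participants whether they had received training when they answered the first post-test. One arm has just attended up to 12 hours of small-group sessions with homework; the other has attended none. The supplied text describes no sham, no attention control and no masking procedure. The documents do not use the term open-label; it follows from this schedule.

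**3. Is baseline affected?** No. Section 4 says: "After pre-testing of the first 10-24 participants, they will be randomly assigned". Pre-test answers are given before anyone has an arm.

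**4. Which outcomes are affected?** All those measured after randomisation, in two grades.

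- *Self-report questionnaires in Table 2:* 6 pain-relevant + 5 adaptive + 3 emotional = 14, counting PACE once. One of these, ACE, records childhood history, so I leave it out: 14 − 1 = 13.
- *Items:* pain 20 + 8 + 8 + 8 + 13 + 8 = 65; adaptive 36 + 14 + 10 + 9 + 47 = 116; emotional 9 + 7 + 10 = 26. The total is 65 + 116 + 26 = 207, and without the 10 ACE items it is 197. The respondent is the assessor, so these are open-label.
- *Neurocognitive tests and the walking measure:* a tester may be blind, but the person performing the test is not. At most these are tester-blind.

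**5. How far does tester blinding reach?** At the first post-test both arms are tested (10-24 per cohort in Table 5), so it is feasible. At the second post-test only delayed-arm participants attend (5-12 per cohort), so attendance itself reveals the arm.

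**The case against.** **The comparator is defined clearly elsewhere.** A whole section is headed Control Condition, and Statistical Considerations names the arm as a delayed-training control group. The comparator phrase in hypothesis (a) may be shorthand for that name. The two Interventionist role descriptions mention 90-minute visits for the control condition; these may be the delayed group's own training visits after the first post-test. This stands. A reader might infer that the plan promises an active or sham control, but the documents do not support that. The wording is ambiguous and needs aligning; it does not establish a second contradiction.

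**A waiting list is reasonable in a pilot.** Agreed. The design is not in dispute, and content would remain mixed with attention and expectation after every edit proposed here. The edits correct what is claimed.

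**Some material is not visible.** Appendix 6, which holds the Blinding Monitor, is not in the supplied text, and consent pages were removed. The exact form of the monitor and what participants are told therefore cannot be checked. That limits comment on the monitor itself. It does not rescue the sentence, since no form can hide from people whether they have attended sessions.

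**Session payments might seem to add a bias.** By the first post-test only the immediate arm can have earned them. But the delayed arm is later offered the same paid sessions and has the higher total, $825 against $750; the $75 difference is its second post-test. The difference in session pay is one of timing, and the point does not rest on it.

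**Conclusion.** The statement that participants are blind contradicts the plan's own design and is wrong as written. It affects the interpretation of every outcome measured after randomisation, including 13 of the 14 questionnaires in Table 2 (197 of 207 items). Baseline scores are not affected, and tester blinding at the first post-test is not challenged.

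Two stronger readings should be resisted. A reader might infer that the self-report results would be false positives at some calculable rate. The documents give no size for an expectation or attention effect, and a difference from these sources is not an error for immediate GRIT against a waiting list, which is the contrast planned. A reader might also infer that only the questionnaires are affected. That is too narrow, because participants also know their arm when they take the neurocognitive and walking tests.

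The conclusion rests on the schedule in the design sections and Table 5 and on no assumed quantity. It should be corrected because it changes what the trial may conclude, although the planned immediate-versus-delayed contrast is already correct.

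**What to change.** 1. **Quality Monitoring of the Study.** Limit the blinding statement to the testers at the first post-test. Note that the arm can be inferred at the second, which only delayed-arm participants take.
2. **Outcome Measures or Statistical Considerations.** State that participants know their arm for all outcomes after randomisation: questionnaires are open-label, and neurocognitive and walking measures are at most tester-blind.
3. **Hypotheses (a) and (b).** Name the comparison as immediate GRIT against waiting list (delayed training), in line with Statistical Considerations and section 7. Add that a difference will not be credited to GRIT content over another training, or presented as a participant-blind result.
4. **Side note.** Align the comparator phrase in hypothesis (a) and the references to control visits in the two Interventionist role descriptions with the Design and Methods text and sections 5 and 7.

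The cost is wording and a more modest claim. Nothing changes in the design, randomisation, sample size or analysis.
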